10.14 Analysis of pharmacokinetic variables

ACT-132577 plasma concentrations and, if applicable, [REDACTED], will be summarized for ACT-132577 treated groups only.

The data will be summarized by active treatment and visit by arithmetic mean, SD of the mean, minimum, maximum, median, coefficient of variation of the arithmetic mean (CV%), and number of observations. For mean value calculations, all values below the limit of quantification (BLQ values) will be set to zero. If $\leq 50\%$ of the values at a given time point are BLQ, these values will be set to zero for calculation of the mean value. If $\geq 50\%$ of the values at a given time point are BLQ, no mean value will be calculated. Additionally, summaries will be created by sex, race and age.

A subject listing presenting ACT-132577 data will also be provided. Data presentations will follow the general rules as described in Section 10.2.

11 GENERAL DEFINITIONS AND DERIVATIONS

11.1 Time windows

To allow analysis of data at the relevant planned (scheduled) visits, all recorded assessments, including unscheduled ones, are re-assigned to the most appropriate visit according to the best fitting time window for that visit [see Table 5]. Note that there are no 'gaps' between the visit windows in order to keep all values in the analysis.

Table 5 Visit time windows

Visit	Target day*	Min. day	Max. day
1	-42	-	-35
2	-28	-34	-18
3	-7	-17	-4
4	1	-3	1
5	14	1	21
6	28	22	42
7 - I	55	43	EOT***
7 - II**	56	EOT + 01 m	EOT + 25 h
8	70	EOT + 25 h 01 m	No limit

* Number of days from start of double-blind treatment.

** Only for ABPM.

*** For OBPM use EOT + 05 m (for the time of the average SiDBP)

ABPM = ambulatory blood pressure monitoring; EOT = End-of-Treatment; OBPM = office blood pressure measurement; SiDBP = sitting diastolic blood pressure.

For assessments for which time is collected, please use the following rules:

- Target day = Target day and time 12:00
- Min. day = Min. day and time 0:00
- Max. day = Max. day and time 23:59

Visit 4 / Day 1

- Target day 1 = Start date/time of DB treatment
- Max. day1 = Start date/time of DB treatment

Visit 5 / Day 1

- Min. day 1 = Start date/time of DB treatment + 1 minute

Visit 7 - I / EOT

- Max. day = End date/time of DB treatment

Visit 7 - II / EOT

- Min. day = End date/time of DB treatment + 1 minute

In the event that there is more than one value within the same time window, the value closest to the planned assessment date will be taken. In the event of equidistant values from the planned time point, the last assessment will be considered for the analyses. Where multiple assessments fall on the same day the latest is then used.

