8.4 Premature End-of-Treatment visit (Visit 9)

All subjects who prematurely discontinue study treatment must have Visit 9 performed as soon as possible but not longer than 7 days after the last dose of study treatment, provided that the subject's consent for this limited participation in the study has not been withdrawn.

Essential hypertension Protocol AC-080A201 Version 3 30 May 2016, page 74/112

Confidential

The following assessments are to be performed at premature EOT / Visit 9:

- Sitting BP and HR, and standing BP, measured by OBPM device.
- Physical examination and body weight.
- *12-lead ECG.
- *Laboratory test (i.e., hematology, blood chemistry, and pregnancy test if applicable).
- *Urinalysis (dipstick by site / UACR by central laboratory).
- Reporting of AEs and SAEs.
- Recording of changes in concomitant medications.
- *Assessment of childbearing potential and recording of changes in contraception methods.
- Check compliance with study treatment.
- Retrieve study treatment bottles.
- Make an appointment for the follow-up telephone call or, *for women of childbearing potential, an appointment for the follow-up visit.
- * If subject discontinued study treatment during run-in period,
- This test may not be performed, and
- For women of childbearing potential, a follow-up telephone call can be made instead of the follow-up visit.

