10.9.4 Laboratory tests

All hematology and chemistry parameters provided by the central and local laboratory are displayed in a subject listing. Marked laboratory abnormalities will be flagged

accordingly. Laboratory values below the limit of detection (i.e., preceded by '<') will be replaced by half that limit in calculations as well as in determining abnormalities.

Hematology, chemistry and urine parameters UACR will be summarized by treatment group for each time window visit. Changes from baseline in these parameters will be summarized for each post-baseline assessment, displaying:

- observed values at baseline and at the post-baseline visit window
- absolute change from baseline to post-baseline visit window

In each evaluation only subjects who had both the assessments at baseline and the considered post-baseline time point are included.

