11.6 Double-blind treatment end date/time

The double-blind treatment end date is the last day of intake of DB study treatment. It is derived from the last DB treatment end date (in chronological order) in the **Study Drug Log** eCRF where the ‘Study Period’ is ‘DB TREATMENT’ and the reason for treatment end is \neq “TEMPORARILY INTERRUPTED DUE TO AN AE” or “TEMPORARILY INTERRUPTED NOT DUE TO AN AE”.

If the study treatment end date is still missing after this derivation, the earliest of the date of Visit 7 - Week 8 / EOT /Part 1 and the date of death (if any) is to be imputed. If the end date is still missing, the EOS date as defined in the Section 2.1 will be used. If the end time of double-blind treatment is missing and DB end date corresponds to the date of the first assessment of ABPM at Visit 7, the time of the first ABPM assessment will be used, otherwise, it will be set to 23:59.

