11 GENERAL DEFINITIONS AND DERIVATIONS

11.1 Time windows

To allow analysis of data at the relevant planned (scheduled) visits, all recorded assessments, including unscheduled ones, are re-assigned to the most appropriate visit according to the best fitting time-window for that visit [see [Table 5](#)].

Table 5 Visit time windows

Visit	Period	Target day	Min day	Max day
1	I: Run-in	-42	-	-35
2		-28	-34	-18
3		-7	-17	-4
4 ^a		-1	-3	-1
5 ^b	II: Double-blind	14	1	21
6 ^b		28	22	42
7 ^b		55	43	EOT
8 ^c	III: Follow-up	70	EOT	No limit

^aMeasurements mapped to Visit 4 must be before randomization; otherwise map to Visit 3

^bMeasurements mapped to Visit 5, 6 or 7 must be before the patient's EOT; otherwise map to Visit 8

^cMeasurements taken on Visit 8 must be after the patient's EOT; otherwise map to Visit 7

EOT = End-of-Treatment.

If more than one assessment falls within the same time window, the closest value to the planned time point will be assigned to the re-mapped visit. In the event of equidistant values from the planned time point, the last assessment will be considered for the analyses.

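### SAP Table 5 has no window for the premature end-of-treatment visit, so off-drug readings can be labelled Week 2, Week 4 or Week 10 in FAS and Safety Set by-visit analyses

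*SAP*

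**What the plan says.** SAP 11.1 sets the rule: "all recorded assessments, including unscheduled ones, are re-assigned to the most appropriate visit according to the best fitting time window for that visit". In Table 5, Visit 5 (Week 2) runs from just after the first double-blind dose to Day 21, with target Day 14. Visit 6 (Week 4) runs from Day 22 to Day 42, with target Day 28. Neither is limited by the subject's end of treatment. Visit 7-I (Week 8) runs from Day 43 and does have such a limit, "Max. day = End date/time of DB treatment", with 5 minutes' grace for office blood pressure. Visit 8 (Week 10, target Day 70) opens at EOT + 25 h 01 min and has no upper limit. EOT is defined in SAP 11.6: "The double-blind treatment end date is the last day of intake of DB study treatment".

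The tie rule is that "In the event that there is more than one value within the same time window, the value closest to the planned assessment date will be" the one used. It deals with several values in one window, not with one value in two windows.

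Protocol 8.4 requires that subjects who stop study treatment early "must have Visit 9 performed as soon as possible but not longer than 7 days after the last dose of study treatment", if consent continues. Protocol 5.1.11 then sends them to safety follow-up, not to the placebo withdrawal period. Table 5 has no row for Visit 9.

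SAP 5.5.3 labels the Visit 5 and 6 windows as Weeks 2 and 4 of double-blind treatment, and the Visit 8 window as week 2 of the withdrawal period. The separate SAP for the sample size re-estimation has a rule that the main SAP lacks: in its Table 5, footnote b, readings mapped to Visits 5, 6 or 7 "must be before the patient's EOT; otherwise map to Visit 8".

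**The concern.** The windows follow one another cleanly only for a subject who reaches Visit 7. For someone who stops early, the Visit 8 window slides back over the fixed Visit 5 and 6 windows, and the SAP does not say which one wins. Neither answer gives a correct label. Under Week 2 or 4, a reading taken up to 7 days off drug counts as on-treatment. Under Visit 8, a subject who never took withdrawal placebo is pooled with subjects about two weeks into it.

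The analyses at stake are:
- the FAS observed-case mixed model for SiDBP and SiSBP (SAP 10.6.4, 10.7), where Weeks 2 and 4 also help predict missing Week 8 values (Table 4, note a);
- the FAS average-over-time analyses;
- the FAS by-visit blood pressure tables;
- the Safety Set by-visit tables of laboratory values, weight and pulse rate. Laboratory parameters, for example, "will be summarized by treatment group for each time window visit" (SAP 10.9.4).

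**Working it through.** The plan gives no figure of its own on this point, so the check applies Table 5 as written.

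**Inputs.** Windows as above (SAP 11.1); Visit 9 up to 7 days after the last dose (Protocol 8.4); half-life about 44 h (Protocol 1.2.1). Assumed dosing and reading time is 08:00; 07:00, 10:00 and the imputed end time of 23:59 (SAP 11.6) were also tried.

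**1. Where the overlap ends.** Last dose on Day 41 at 08:00: Visit 8 opens on Day 42 at 09:01 and Visit 6 closes on Day 42 at 23:59, an overlap of 14 h 58 min. Last dose on Day 42 at 08:00: Visit 8 opens on Day 43 at 09:01, so there is no overlap. The last EOT day with overlap is Day 41 for doses from 07:00 to 10:00, and Day 40 if the end time is imputed as 23:59.

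**2. Readings 2 to 7 days after the last dose, EOT Days 1-42.** There are 42 × 6 = 252 combinations of days. These are combinations, not subjects.
- In both Visit 5 and Visit 8: 14 × 6 + (5+4+3+2+1) = 99.
- In both Visit 6 and Visit 8: (35 × 6 + 15) − 99 = 126.
- In Visit 8 only: 252 − 225 = 27.
- In an off-treatment category: 0.

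So 225/252 = 89% lie in two windows. If the nearest target day decides, all 225 become Week 2 or Week 4. Under the re-estimation SAP's footnote, all 252 become Visit 8.

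**3. Later premature stops.** For EOT Days 43-54, all 12 × 6 = 72 combinations fall in Visit 8 only.

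**4. Effect of the closest-value rule.** Suppose Visits 5 and 6 took place on Days 14 and 28 while the subject was still treated. The on-schedule value then beats the Visit 9 value for EOT Days 14-19 with a reading by Day 21 (6+5+4+3+2+1 = 21) and for EOT Days 28-40 with a reading by Day 42 (8 × 6 + 5+4+3+2+1 = 63). That removes 84 of the 225 (37%) and leaves 141. The rule can also work the other way. With Visit 6 and the last dose on Day 25 and Visit 9 on Day 29, the distances to target Day 28 are 3 days and 1 day, so the off-drug value is used.

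**5. How far off drug.** Relative to the 24-hour steady-state trough, the concentration left d days after the last dose is 0.5^((d−1)×24/44). This gives 69% at d = 2, 22% at d = 5 and 10% at d = 7.

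**6. Which analyses can be reached by a stop before Day 43.** SAP section 6 excludes double-blind duration under 49 days from the PPS, so these subjects are in none of the PPS analyses, including the Week 2/4/8/10 mixed model (SAP 10.8, 13.8). Their Visit 7-I window is empty, so they do not enter the Week 8 hemoglobin and weight MCP-Mod analyses. Treatment-emergent tables run to EOT + 30 days regardless of visit.

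**The case against.** The best defence is that little of consequence is touched. The primary analysis is clean, SAP 10.1 calls everything else exploratory, and the closest-value rule often lets the scheduled value prevail. All of that stands and limits the weight of the point.

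A second defence is that SAP 11.1 wants no gaps so that every value is kept, and that an FAS analysis by assigned treatment may properly include values after discontinuation. That would be a legitimate choice, but Table 5 does not make it consistently: Week 8 is cut off at EOT while Weeks 2 and 4 are not. Nor does it justify the Week 10 label. Protocol 11.3.5 limits withdrawal-period safety analyses to subjects who took part in that period, and SAP 10.9 does not carry this over.

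Three stronger readings are tempting and not supported:
- *Recovery of blood pressure after withdrawal becomes unreadable.* The Week 10 model is PPS only, so stops before Day 43 do not enter it; the FAS descriptive blood pressure tables are what is exposed.
- *Up to 20 subjects per arm are affected*, from 90 randomized less 70 in the PPS. PPS losses also include poor compliance, interfering medication and an invalid Week 8 value. Visit 9 needs continuing consent and may fall within 25 h of the last dose. Randomization was also reduced to 490 (SAP 4.2).
- *The effect is diluted in proportion to concentration.* The documents give no offset time for blood pressure, hemoglobin or weight.

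**Conclusion.** The defect holds and should be corrected, with limited reach. Table 5 gives a premature-EOT reading taken more than 25 h after the last dose no correct home. For EOT up to about Day 41 it can fall in two windows with no rule to choose between them; for later premature stops it becomes Week 10. It is mislabelled whenever no value closer to target fills the window.

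The primary PPS analysis, the other PPS analyses, the Week 8 hemoglobin and weight MCP-Mod analyses and the treatment-emergent tables are not affected by subjects stopping before Day 43. Whether a Visit 9 reading may serve as the FAS LOCF value is left open: Protocol 11.3.2.2 carries forward the last post-baseline measurement and does not address readings off treatment.

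The 89% describes combinations of days under assumed clock times and says nothing about frequency. Neither the number of subjects affected nor the size of any bias can be derived from the documents.

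**What to change.** In SAP 11.1:

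1. Map to Visits 5 and 6 only assessments taken no later than EOT + 25 h. Leave the Visit 7-I limit as it is (EOT, or EOT + 5 min for office blood pressure). The last dose is taken at Visit 7 Part 1 after the trough reading, so a later limit could admit post-dose values to the primary endpoint window.
2. Map to Visit 8 only assessments of subjects with an 'SB WITHDRAWAL' record in the Study Drug Log.
3. Put all other post-EOT assessments in a separate premature-EOT/post-treatment row, excluded from the Week 2, 4 and 10 summaries and from the mixed models. State whether that row can supply the FAS LOCF value.

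Treatment-emergent abnormality tables continue to use all values. Applied to the 252 combinations, these rules leave no double assignment, no false Week 2 or 4 and no false Week 10. Copying the re-estimation SAP's footnote alone would also remove the overlap, but would send all 252 to Week 10.

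The cost is a few lines of text and one derivation flag from data already collected. The downside is slightly fewer values in the Week 2, 4 and 10 columns.

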8.2.4 Visit 7 / Week 8 DB-EOT

The assessments of this visit will be performed over 2 consecutive days.

Visit 7 / Part 1 is the end of DB treatment period. On this day, the EOT 24-h ABPM under DB study treatment will be performed.

Visit 7 / Part 2 is the start of the SB placebo withdrawal period.

8.2.4.1 Visit 7 / Part 1

Visit 7 / Part 1 must be scheduled at Day 55 ± 5 days.

Part 1 includes:

- Sitting BP and HR, and standing BP, measured by OBPM device at trough.
- Physical examination and body weight.
- 12-lead ECG.
- Laboratory test (i.e., hematology, blood chemistry, and pregnancy test if applicable).
- |
- Urinalysis (dipstick by site / UACR by central laboratory).
- Reporting of AEs and SAEs.
- Recording of changes in concomitant medications.
- Assessment of childbearing potential and recording of changes in contraception methods, if applicable.
- Record the date and time of last study treatment intake before this visit.
- Check compliance with study treatment.
- Apply the ABPM device according to the BP manual for 24-h recording and review the subject's instruction handout with the study participant.
- Intake of the last doses of the DB period study treatment and retrieve study treatment bottles. Record the study treatment intake date and time.
- Instruct subject to return to the site in the next morning.

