4.2 Changes in the conduct of the study / data collection

A blinded sample size re-estimation was introduced in Version 3 of the protocol. This sample size re-estimation was based on the standard deviation (SD) of the primary endpoint, change from baseline to Week 8 in DBP as measured by OBPM in the PPS. As a consequence the number of randomized subjects was lowered to 490 (instead of the foreseen 540). The lower sample size did not affect the conduct of the study or the analysis of the data.

After database lock but before unblinding, it was noticed that one subject who had a Week 8 sitting diastolic blood pressure (SiDBP) outside of the analysis window was, however, included in the PPS (after accounting for the protocol deviations [PDs] present in the database). The decision was taken by management not to unlock the database and to maintain the PPS as it was. The subject remained in the PPS, with a missing value for the Week 8 SiDBP.

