10.2 General rules for data presentations

This section describes the general rules applied for all data displays.

SAS version 9.3 is used for the statistical analyses except for the primary endpoint (dose-response analysis) that is analyzed by means of the R package.

Unless otherwise specified in this document:

- All listings are sorted by randomized treatment, subject number and, when appropriate, by visit / date of assessment. If a listing includes non-randomized subjects, these will appear after the randomized subjects. All data collected are displayed, including unscheduled visits (if any).
- In summary tables and graphical representations, subjects are grouped by randomized treatment group, except for the SAF for which the actual treatment is used.
- In summary tables based on the RND, FAS, PPS and SAF, the order of the treatment groups is: placebo, ACT-132577 5 mg, ACT-132577 10 mg, ACT-132577 25 mg, ACT-132577 50 mg and Lisinpril 20 mg, followed by Total (if required). In summary tables based on the RIS or SCR, only a total column will be given.

- The absolute change from baseline to Visit X is defined as the difference between the post-baseline Visit X value and the baseline value.
- In order to analyze the data at the relevant planned (scheduled) visits, all recorded assessments for each subject up to the Week 10 visit are reassigned to the most appropriate visit according to the time window for that visit. The windows are consecutive (i.e., there are no gaps) and are based on the study day corresponding to the date of assessment. Any unscheduled visit is also mapped to a time window. Details of the visit mapping are given in Section 11.1.
- According to section 11.3.2.2 of the protocol, imputation rules for missing data are defined for the evaluation of efficacy endpoints at Week 8. Subjects without a value in the defined Week 8 time window are included in the analysis according to the rules highlighted in Section 9.

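### With EOT on Day 43 or later, SAP Table 5 gives office BP readings from EOT + 6 min to EOT + 25 h no visit, so a valid Visit 7 trough is lost from Week 8 if the Visit 7 dose is not taken (minor)

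*SAP*

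**What the plan says.** - SAP 11.1, Table 5: Visit 7-I runs from Day 43 to EOT, with an office BP exception: "For OBPM use EOT + 05 m (for the time of the average SiDBP". Visit 7-II (EOT + 1 min to EOT + 25 h) is reserved for ABPM. Visit 8 starts at EOT + 25 h 01 min.
- SAP 10.2 on the same windows: "The windows are consecutive (i.e., there are no gaps". SAP 11.1 likewise says that there are none "between the visit windows in order to keep all values in the analysis".
- SAP 11.6 ties EOT to actual intake: "The double-blind treatment end date is the last day of intake of DB study treatment".
- Protocol 8.2.4.1 lists the trough office BP first at Visit 7 Part 1 and, near the end of the visit, "Intake of the last doses of the DB period study treatment and retrieve study treatment bottles".
- SAP 5.5.1 defines the primary endpoint on trough SiDBP, 24 hours after dosing, and takes Week 8 to be the Visit 7 window.
- SAP 6 excludes from the PPS any subject without a valid Week 8 SiDBP.
- SAP 4.2 reports one PPS subject whose Week 8 SiDBP was outside the analysis window: "The subject remained in the PPS, with a missing value for the Week 8 SiDBP".

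**The concern.** The table and the two sentences describing it cannot both be right. Most of the unassigned stretch is harmless, because an office reading taken after the Visit 7 dose is not a trough and should stay out of Week 8. The exception is a subject who attends Visit 7, has the trough measured as planned, and then does not take the dose. EOT is then the previous intake, and the cut-off that was meant to keep post-dose readings out removes a proper pre-dose trough. The subject either leaves the PPS, which is the primary analysis set, or stays in it with no primary value. In the FAS the subject remains, but with an earlier value carried forward in place of an observed Week 8 trough.

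**Working it through.** **1. Length of the unassigned stretch.** The stated gap is zero. From Table 5, for office BP:
- last minute of Visit 7-I: EOT + 5
- first minute of Visit 8: EOT + 25 × 60 + 1 = EOT + 1,501
- unassigned: EOT + 6 to EOT + 1,500, that is 1,500 − 6 + 1 = 1,495 minutes (24 h 55 min)

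ABPM has no such gap, because row 7-II covers it.

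**2. Dependence on EOT day.** The Visit 5 and Visit 6 windows are not capped at EOT and together run to Day 42. With an earlier EOT, post-EOT readings fall into those windows. With EOT on Day 42 the gap is partial: for EOT at 08:00, minutes 960 to 1,500, or 541 minutes. The full 1,495 minutes apply for EOT on Day 43 or later.

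**3. Planned sequence.** Reading at 08:30 and dose at 09:00 on Day 55: the reading precedes EOT and maps to Visit 7-I. There is no problem.

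**4. Visit 7 dose not taken.** Last dose at 08:00 on Day 54, reading at 08:00 on Day 55: the reading is at EOT + 1,440 min, later than + 5 and no later than + 1,500, so it has no window. If the EOT date is the previous day but its time is missing and set to 23:59 (SAP 11.6), a 07:00–10:00 reading is about 7 to 10 h after EOT and is also unassigned.

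**5. Which window it misses.** Assume dose and reading are independent and uniform over 07:00–10:00. The interval is then 21 to 27 h, and P(> 25 h) = (3 − 1)² / (2 × 3²) = 2/9 = 22%. So about 78% of such readings have no window and 22% go to Visit 8; none reach Week 8. The split depends on the assumed clock times, because Protocol 7.2.1 adds ± 10 h to the 07:00–10:00 measurement window.

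**6. Whether another PPS rule already removes these subjects.**
- Duration: Visit 7 is Day 55 ± 5, so the last dose is on Day 49 to 59. The shortest duration is 49 − 1 + 1 = 49 days, which is not below 49.
- Compliance: SAP 5.3.2 sets expected capsules at duration × 2, and duration stops at the last dose. For a last dose on Day 54 this is 54 × 2 = 108 expected and 108 taken, or 100%.
- The remaining limb of exclusion 5, treatment not taken according to protocol, may catch some of them.

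**7. Precision.** If a fraction p of subjects lose the value at random, the standard error rises by 1/√(1 − p) − 1. For p = 0.01 this is 1/√0.99 − 1 = 0.5%. With 490 randomized (SAP 4.2), the five dose-response arms hold 490 × 5/6 = 408 subjects, so 1% is about 4 values.

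**The case against.** The strongest reply is that SAP 5.5.1 itself equates Week 8 with the Visit 7 window. A reading outside that window is a trough but not a Week 8 value as defined, so nothing meeting the definition is discarded. That is formally correct, but it moves the fault into the window. The reading comes from the scheduled Week 8 visit, before any further dose, and Table 5 leaves it out for a reason unrelated to its validity.

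A second reply is that SAP 5.5 and 11.1 assign every assessment to the most suitable visit. Table 5 nevertheless has fixed limits and no rule for values between them. The separate SAP for the sample size re-estimation does have one: it sends readings after EOT to Visit 8.

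Third, the harm needs a departure from the planned on-site dose, and no document reports one. This stands, and it is why the point is minor. It also stands that a missing treatment end date is imputed from the Visit 7 Part 1 date or date of death, whichever is earlier (SAP 11.6). When the visit date is used, the trough normally maps correctly. That helps only when the date is missing, not when an earlier date is recorded.

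A reader might infer that the subject in SAP 4.2 was lost through this gap. The SAP gives neither the cause nor whether the reading was a trough. A reading taken after the Visit 7 dose would look the same.

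**Conclusion.** The point holds, as minor. For office BP with EOT on Day 43 or later, Table 5 contradicts both statements that no gap exists. When the Visit 7 dose is not taken, it removes a valid pre-dose trough from the primary Week 8 analysis. The contradiction follows from the text alone. The effect on the analysis rests on an event whose frequency is undocumented and probably very small. The main cost is precision, about 0.5% on the standard error per 1% of subjects, if the losses are unrelated to outcome.

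A reader might go further and infer bias. If grade 3 blood pressure were confirmed at Visit 7 before dosing, the dose might be withheld, and high readings would then be lost preferentially. The documents do not support giving this a size or an upper bound. Protocol 5.1.12 leaves the timing of re-measurement to the investigator and allows a systolic as well as a diastolic trigger. Neither document reports how often this happened at Visit 7 or whether the dose was then withheld.

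**What to change.** Add to the Table 5 footnote that an office BP reading from the scheduled Visit 7 Part 1, taken the day after the last double-blind dose and before any further study dose (double-blind or withdrawal placebo), maps to Week 8 even if it is later than EOT + 5 min, and is not also used for Visit 8. State that all other office readings between EOT + 5 min and EOT + 25 h are listed but not mapped. This keeps readings after the Visit 7 dose out of Week 8. It also gives no entry to premature end-of-treatment readings, for which Protocol 8.4 specifies only "Sitting BP and HR, and standing BP, measured by OBPM device" without requiring trough. Correct the sentences in SAP 10.2 and 11.1 that deny any gap.

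The cost is one footnote, one added statement, two corrected sentences and a re-run of the derived visit mapping before unblinding. No database unlock is needed. For the out-of-window subject in SAP 4.2, "The decision was taken by management not to unlock the database and to maintain the PPS as it was". If the locked PPS is kept here too, report the re-mapped result as a sensitivity analysis. No clinical rule is changed.
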